### 5.1.3 Definition of Dose-Limiting Toxicity (DLT)

---

Toxicities will be graded according to the NCI Common Terminology Criteria for Adverse Events version 4.0. **All patients receiving any number of NSCs will be evaluated for dose limiting toxicity criteria.**

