## Assigning Treatment and Correlative Study Regimen

---

A participant's starting NSC dose level, irinotecan dose schedule, correlative study procedures, and NSC regimen will be assigned by the Principal Investigator based on the following criteria:

1. Except where planned in the expansion cohort, participants who do not receive Day 1 NSCs will be replaced.
2. During the 3+3 stage of the trial, any participants who are not evaluable for dose escalation will be replaced.
3. During the 3+3 stage of the trial, the NSC dose level (-1,1,2,3, or 4) and irinotecan dose schedule (A, B, or C) will be determined using criteria defined in Section 5.3.
4. The first six patients enrolled to the trial will have microdialysis catheters inserted and undergo microdialysis and accompanying blood plasma PK studies. If one or more of the six patients does not receive cycle 1 day 3 irinotecan, the patient(s) will be replaced with the next patient(s) enrolled.
5. During the expansion cohort, all eight participants will have microdialysis catheters inserted and undergo microdialysis and accompanying blood plasma PK studies. N.B., since it is anticipated that the MTD/MFD will be 150 million NSCs (dose level 4), the 6 patients who will be treated on dose level 4 will undergo intracerebral microdialysis and be counted as part of the expansion cohort.
6. During the expansion cohort, all 8 participants will follow the NSC dose level and irinotecan dose schedule per the MTD (or if the MTD is not reached, the MFD), however 4 participants will receive their initial NSC administration on the day of surgery (Day 1), and 4 participants will receive their first NSC administration on Day 15. Participants will be grouped according to surgery type (craniotomy or biopsy). As each group enrolls participants, it will alternate between enrolling the participant to the Day 1 NSC start date and the Day 15 NSC start date. (See Section 5.4 for further explanation).

Based on the above criteria, the Principal Investigator will communicate to the clinical research team and the neurosurgeon the assigned biopsy or craniotomy procedure A-K as detailed in table 8.2a and table 8.2b.

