**A DLT is defined as an adverse event that:**

- (a) is related to the administration of NSCs, irinotecan or the combination of NSCs with irinotecan, with an attribution of possible, probable, or definite, and
- (b) occurs during the first treatment cycle (including Cycle 2 Day 1 safety assessments), and
- (c) meets any of the following criteria:

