#### **Treatment Plan: Expansion Cohort**

---

After the MTD/MFD of the combination therapy is defined, an expansion cohort of 8 patients will be treated to gain more experience regarding the tolerability of study treatment at the MTD/MFD and to assess the biological activity of the hCE1m6-NSCs using intracerebral microdialysis. Since it is anticipated that the MTD/MFD will be 150 million NSCs (dose level 4), the 6 patients who will be treated on dose level 4 will undergo intracerebral microdialysis and be counted as part of the expansion cohort.

Four patients in the expansion cohort will undergo intracerebral microdialysis after receiving NSCs at the time of surgery followed 2 days later by IV irinotecan, but the other 4 patients in this cohort will not receive NSCs on the day of surgery. Instead they will be given IV irinotecan 2 days after surgery, and dialysate samples will be collected from them to determine how much SN-38 is present in the brain from treatment with IV irinotecan alone. These 4 patients will then receive their first dose of NSCs through the Rickham on day 15 of cycle 1 followed by irinotecan on day 17.

To determine who will receive their initial NSCs administration on the day of surgery, and who will receive their first NSC administration on Day 15 via the Rickham catheter, participants will be stratified according to surgery type (craniotomy or biopsy), and, as each group enrolls participants, it will alternate between enrolling the participant to the Day 1 NSC start date and the Day 15 NSC start date. For example, the first craniotomy participant will be assigned Day 1 NSC start date, the second craniotomy participant will be assigned Day 15 NSC start date, the third will be assigned Day 1 NSC start date, the fourth will be assigned Day 15 NSC start date, and so on as applicable. The same alternate enrollment scheme will apply to participants undergoing the biopsy procedure. The rationale for this plan is to ensure to the degree possible an even distribution of start dates for each surgery group which should increase the ability for direct comparison. There is no requirement for specific number of biopsy or craniotomy participants in the expansion cohort.

If the DLT rate in the expansion cohort exceeds 34%, the toxicity data will be reviewed.

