### 7.1.5 General Information

---

1. The study will use the NCI Common Terminology Criteria for Adverse Events (CTCAE) version 4.0 to grade toxicities. A copy of the version 4.0 can be downloaded from:  
<http://evs.nci.nih.gov/ftp1/CTCAE/About.html>
2. Whenever treatment is held pending resolution of toxicity to grade 1 or return to baseline, this criterion may also be met if the toxicity resolves to within 1 grade of the baseline value for a pre-existing laboratory abnormality. Baseline values are from screening assessments.
3. Study agents are always held together, regardless of the attribution of the toxicity.
4. NSC or irinotecan dose re-escalation is never permitted in this study.
5. If, for the best interest of the patient, the investigator wants to hold the study agent(s) or dose reduce (including increasing the dose reduction) after an adverse event in a manner not outlined in Table 7.2.4, this is permissible following discussion with and written approval the Principal investigator.\*
6. For situations where a participant experiences a toxicity which the treating investigator feels is unlikely related to treatment with either study agent, but which requires hold or reduction of either agent according to Table 7.2.4, maintaining treatment or maintaining treatment dose is allowable per discussion with and written approval by the Principal Investigator.\*
7. For holds due to toxicities related to study agent(s), if the participant does not meet criteria to resume treatment within 28 days of their last NSC administration (or irinotecan for Dose Level 1/1 participants after they have completed cycle 1), the participant must permanently discontinue study treatment (both agents). However, if the participant is clearly benefiting from the study, the investigator may contact the Principal Investigator to determine if the participant can remain on study and at what dose level. Agreement of the Principal Investigator is to be documented in writing.\*
8. For holds for reasons other than treatment related toxicities, such as inclement weather or adverse events unrelated to study agents, if the participant does not meet criteria to resume treatment within 28 days of their last NSC administration, the study agent(s) may be restarted with written approval from the Principal Investigator, as long as there has been no significant evidence of disease progression during the treatment interruption.\*

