#### 15.1.6 Analysis Plan:

---

Tables will be created to summarize all toxicities and side effects by dose, course, organ severity (by NCI CTCAE version 4.0), and attribution. Rates and associated 95% Clopper Pearson confidence limits will be estimated for DLTs and clinical benefit at the RP2D. Descriptive statistics will be provided for study patient demographics.

Pharmacokinetic data from patients who undergo intracerebral microdialysis will be summarized using descriptive statistics and graphical methods. The biologic activity of the hCE1m6-NSCs, based on comparison of microdialysis SN38 PK data from patients receiving NSCs + irinotecan vs patients receiving irinotecan alone, will be assessed using a one-sided two-sample t test. Regression analysis will be used to assess the relationship between hCE1m6-NSC dose and SN-38 concentrations in brain interstitium using microdialysis data from the patients treated with the initial NSC dose (n=6) and from the patients in the expansion cohort treated with the highest NSC dose (n=4). Other secondary objectives include assessing for possible development of NSC immunogenicity after first and repeat exposures, and—when feasible—evaluating the fate of the NSCs at autopsy. These results will be summarized using descriptive statistics and graphical methods.

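### Section 5.3.3 names only NSC recipients as evaluated for DLT, which leaves open whether a Day 15-start expansion patient who stops for irinotecan toxicity before any NSCs enters the DLT rate

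*Combined protocol and SAP*

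**What the plan says.** Section 5.3.3 (Definition of Dose-Limiting Toxicity) opens with the evaluated set: "All patients receiving any number of NSCs will be evaluated for dose limiting toxicity criteria". It then defines a DLT as a cycle 1 event that "is related to the administration of NSCs, irinotecan or the combination of NSCs with irinotecan, with an attribution of possible, probable, or definite" and that meets one of the listed criteria. These include receiving less than 80% of study treatments because of toxicity from either agent, and a grade 3 non-hematological, non-nervous-system toxicity that leads to permanent removal from treatment (item 9).

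Section 5.4 (Expansion Cohort) splits eight patients into four with NSCs at surgery and four who have irinotecan on Day 3 without NSCs. Of the second four it says: "These 4 patients will then receive their first dose of NSCs through the Rickham on day 15 of cycle 1 followed by irinotecan on day" (the quote breaks off before the day number, which is 17). Section 5.2, item 1, exempts them from replacement: "Except where planned in the expansion cohort, participants who do not receive Day 1 NSCs will be replaced".

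Two rules link irinotecan toxicity to the later NSC dose. Section 7.2.1, item 3: "Study agents are always held together, regardless of the attribution of the toxicity". Section 5.1, item 8, ends all study treatment for anyone who discontinues irinotecan.

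Two results use the DLT rate. Section 5.4 calls for a review of the toxicity data if the rate in the expansion cohort is above 34%. The Analysis Plan in Section 15.3 says: "Rates and associated 95% Clopper Pearson confidence limits will be estimated for DLTs and clinical benefit at the RP2D". Neither states a denominator. The Sample Size section bases its precision on 14 patients at the MTD/MFD.

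**The concern.** The sentence on who is evaluated suits the 3+3 stage, where a patient without Day 1 NSCs is replaced. The expansion cohort departs from that design on purpose: half of it is exposed to irinotecan for about 12 days (Day 3 to Day 15) before any NSCs.

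Suppose such a patient has a grade 3 irinotecan toxicity in that interval and is permanently taken off treatment. By Section 5.3.3, item 9, this is a DLT. By Section 5.1, item 8, the patient never receives NSCs and so is outside the set that the opening sentence names. The same event in a Day 1-start patient is inside it. The possible omission is therefore informative: the patient is lost because of the toxicity, so the literal rate can only err downward.

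At stake are the DLT rate at the RP2D, which belongs to the primary endpoint, and the 34% review. The stopping rule in Section 5.6 does not cover this case. It counts only DLT-level toxicities probably or definitely attributable to NSCs, or to NSCs with irinotecan, so an event from irinotecan alone is outside it.

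**Working it through.** **1. The plan's own precision figures.** Inputs (Sample Size section): n = 6 with margin 0.38 and 82% detection of a 0.25 rate; n = 14 with margin 0.27 and 90% detection of a 0.15 rate. The margin is the largest half-width of the 95% Clopper-Pearson interval over all possible counts. Detection is the chance of at least one event, 1 − (1 − p)^n.

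- n = 6: margin 0.382; 1 − 0.75^6 = 0.822.
- n = 14: margin 0.270; 1 − 0.85^14 = 0.897.

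All four figures reproduce. With one patient left out, n = 13 gives 0.278 and 1 − 0.85^13 = 0.879. The stated precision therefore counts all 14, including the four Day 15-start patients.

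**2. Which patients are affected.**

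| Day 15-start patient with irinotecan toxicity after Day 3 | Ever receives NSCs? | In the set named in 5.3.3? |
|---|---|---|
| Held, resumes by Day 22 (Section 7.3) | Yes, in cycle 1 | Yes |
| Held longer, resumes in the next cycle (Section 7.3) | Yes, in cycle 2 | Yes |
| Permanently discontinued before any NSCs (Section 5.1, item 8) | No | Not named |

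Only the last row is a problem. Table 7.2.4 prescribes hold-then-resume for grade 4 thrombocytopenia, grade 4 neutropenia, febrile neutropenia and grade 3 or 4 diarrhea, so those events do not by themselves lead to the last row.

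**3. The 34% review.** 0.34 × 8 = 2.72, so at least 3 DLTs among 8 are needed.

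| All patients counted | Omitted | Literal count | Review? |
|---|---|---|---|
| 3/8 = 37.5% (95% CI 8.5–75.5%) | 1 | 2/7 = 28.6% (3.7–71.0%) | Yes becomes no |
| 4/8 = 50.0% | 1 | 3/7 = 42.9% | Yes stays yes |
| 4/8 = 50.0% | 2 | 2/6 = 33.3% | Yes becomes no |

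**4. The RP2D rate.** Taking one DLT patient out of both numerator and denominator changes x/n to (x − 1)/(n − 1). The difference in cross-products is n(x − 1) − x(n − 1) = x − n, which is negative unless every patient has a DLT. So the rate always falls otherwise. On the plan's 14 patients, 3/14 = 21.4% becomes 2/13 = 15.4%, and 5/14 = 35.7% becomes 4/13 = 30.8%.

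**5. Average effect, on assumed values only.** Let p be the true DLT rate and q the chance that a Day 15-start patient has an irinotecan DLT that permanently prevents NSCs. The documents give neither. The approximate literal rate is (np − 4q)/(n − 4q). For example, with n = 8, p = 25% and q = 2%: (2 − 0.08)/(8 − 0.08) = 24.2%, a relative change of −3%. The chance of triggering review is computed exactly for eight newly enrolled, independent patients.

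| p | q | Relative bias, n = 8 | Relative bias, n = 14 | Chance of review: all counted → literal |
|---|---|---|---|---|
| 25% | 2% | −3% | −1.7% | 32.1% → 29.7% |
| 25% | 5% | −8% | −4% | 32.1% → 26.0% |
| 25% | 10% | −16% | −9% | 32.1% → 20.3% |
| 33% | 10% | −11% | −6% | 52.4% → 39.8% |
| 33% | 20% | −23% | −12% | 52.4% → 27.7% |

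The ratio q/p is the share of these patients' DLTs that come before NSCs and end treatment: 8%, 20%, 40%, 30% and 61% in the five rows. Because most listed toxicities are managed by hold and resume, the higher shares look extreme.

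**The case against.** The strongest reply is that the sentence says all patients with NSCs are evaluated, not only those patients. Its reference to any number of NSCs reads naturally as a guard against dropping partly dosed patients. The definition beneath it has no NSC-exposure condition, since it is enough that the event "is related to the administration of NSCs, irinotecan or the combination of NSCs with irinotecan". For dose escalation, Section 5.3.2 counts any patient who has had a DLT. The Sample Size figures count all 14. On this view the sponsor already means to include the patient. This stands as evidence of intent, and it is why a reader who infers that the protocol expressly excludes such patients goes too far. It does not settle the matter: the only sentence on the evaluated set leaves them out, and neither use of the rate has a stated denominator.

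A second reply is that a missed Day 15 dose usually does not mean no NSCs. That also stands. A reader might infer that any irinotecan DLT between Day 3 and Day 15 removes the patient. Table 7.2.4 and Section 7.3 do not support this, because held patients can resume and receive NSCs later.

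A third reply is that little depends on it. The 34% rule prompts a review and does not stop the trial, all enrolled patients are followed for toxicity, all toxicities are tabulated by attribution, and the protocol management team reports quarterly to the data and safety monitoring committee. The event would therefore be seen. The rate reported for the primary endpoint could still differ between two analysts working from the same data.

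**Conclusion.** The point holds as a conflict within the protocol. Section 5.3.3 names an evaluated set based on NSC exposure, while its own DLT criteria and the Sample Size section imply a set that includes patients exposed to irinotecan only. The literal reading can drop a patient because of a DLT, and it biases the rate downward.

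The reach is narrow. It concerns Day 15-start patients who never receive NSCs, at most four of the planned eight. The review is missed only near the threshold, for example at three DLTs with one omitted or four with two omitted.

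A reader might infer a sizeable average bias from the larger rows in the illustration. The documents do not support any value of q; at q = 2% with p = 25% the bias is about −3% on 8 patients and −1.7% on 14, so it may be small.

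A reader might also infer that the MTD decision is affected, because Section 5.4 counts the six dose level 4 patients in the expansion cohort. That would need some of them to be Day 15-start, and the Section 5.3.2 rule that a patient with a DLT counts weighs against it. It is a possibility to close, not an established error.

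**What to change.** - **Section 5.3.3:** reword the opening sentence so that DLT evaluation covers every patient who received any study agent, whether NSCs or irinotecan.
- **Section 5.4 and the Analysis Plan in Section 15.3:** state that the 34% review and the RP2D DLT rate use every patient who received either agent and who either had a DLT or completed the DLT window.
- **Reporting:** list DLTs that occurred before any NSC exposure separately, so that readers can tell them from DLTs after the combination.

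This takes a few sentences and no new data. The downside is that the reported DLT rate may be slightly higher and will include some exposure to irinotecan alone. The separate listing makes that visible.

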**A DLT is defined as an adverse event that:**

- (a) is related to the administration of NSCs, irinotecan or the combination of NSCs with irinotecan, with an attribution of possible, probable, or definite, and
- (b) occurs during the first treatment cycle (including Cycle 2 Day 1 safety assessments), and
- (c) meets any of the following criteria:

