### 5.1.2 Phase I Cohorts and Dose Escalation and De-escalation Criteria

Phase I Cohorts will be of 3 or 6 participants, as indicated by the dose-escalation criteria.

**Enrollment of the first 3 patients to a dose level will be staggered** by requiring that each of the first 3 patients be separately observed for 4 weeks (or until the DLT assessment period has ended) before the next patient can start treatment on that dose level.

Dose escalation will proceed through the identified doses without skipping any dose levels.

**To be counted for dose escalation**, a study patient must receive at least 80% of the assigned NSCs and 80% of the irinotecan for a particular dose level and be followed for 4 weeks OR have experienced a DLT as defined in Section 5.3.3.

All study patients enrolled are to be fully followed for toxicity; any study participant who is not evaluable for dose escalation will be replaced.

The NSC dose levels and irinotecan dose schedules are provided in Table 5.3.1. The first cohort will start at NSC dose level 1 and irinotecan schedule A.

The following dose escalation rules will be used, using the DLT definition as provided in Section 5.3.2:

- If 0/3 study participants experiences a DLT, the next cohort of 3 study patients will be treated at the next higher dose level.
- If 1/3 study participants experiences a DLT, the cohort will be expanded by another 3 study participants who will be treated at the same dose level for a total of 6 study participants.
- If 1/6 participants experiences a DLT, the next cohort of 3 study participants will be treated at the next higher dose level.
- If 2 or more participants of either a 3 participant or 6 participant cohort encounter a DLT, then the MTD has been exceeded. If applicable, three (more) participants will be enrolled at the next lower dose level.
- At least 6 patients will be treated at the MTD (or MFD, if the MTD is not reached).

If the 3+3 design rules indicate a need for de-escalation, the following will apply:

- If all DLTs in a dose level are attributed uniquely to irinotecan, then only the irinotecan schedule will de-escalate.
- If all DLTs in a dose level are attributed uniquely to NSCs, and are not attributed to 'NSCs with irinotecan', nor to irinotecan alone, then only the NSC dose level will de-escalate.

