#### Discontinuation toxicities

1. Receives less than 80% of study treatments due to a toxicity related to NSCs or irinotecan, except CNS toxicities that are present at baseline and attributable to the location of the tumor or the neurosurgery.

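### Four of the eight expansion patients have only one NSC dose inside the cycle-1 DLT window, yet they are pooled with two-dose patients in the DLT rate, the 34% review trigger and the n=14 precision figures

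*Combined protocol and SAP*

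**What the plan says.** In the protocol's Definition of Dose-Limiting Toxicity, clause (b) requires that the event "occurs during the first treatment cycle (including Cycle 2 Day 1 safety assessments), and". Footnote d to the Study Activity Calendar (Table 10) places the Cycle 2 Day 1 assessments before that day's NSC dose.

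Dose levels 2 to 4 give NSCs on Days 1 and 15 of each cycle. In the expansion cohort, half of the eight patients omit the Day 1 dose so that irinotecan alone can be sampled by microdialysis. Section 5.4 (Treatment Plan: Expansion Cohort) then says: "These 4 patients will then receive their first dose of NSCs through the Rickham on day 15 of cycle 1".

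These patients stay in the DLT assessment: "All patients receiving any number of NSCs will be evaluated for dose limiting toxicity criteria". They are also exempt from replacement: "Except where planned in the expansion cohort, participants who do not receive Day 1 NSCs will be replaced". The dose-escalation rules set an exposure minimum, that "a study patient must receive at least 80% of the assigned NSCs and 80% of the irinotecan for a particular dose level", but it is written for escalation. None is stated for the expansion cohort.

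The DLT data at the MTD/MFD are used in three places:

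- Section 5.4: "If the DLT rate in the expansion cohort exceeds 34%, the toxicity data will be reviewed".
- The Analysis Plan in Section 15: a DLT rate at the RP2D with 95% Clopper-Pearson limits, with no split by NSC start day.
- Section 15.1 (Sample Size): 6 + 8 = 14 patients at the MTD/MFD, a maximum margin of error of 0.27, and about a 90% chance of detecting a 0.15 toxicity rate.

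Sections 5.2 and 5.4 also say that, if level 4 is the MTD/MFD as expected, "the 6 patients who will be treated on dose level 4 will undergo intracerebral microdialysis and be counted as part of the expansion cohort". That would make the total 8, not 14.

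**The concern.** The primary objective bases the RP2D partly on toxicity from repeat NSC doses. The earlier human study of the parent cell line gave a single dose, and the background section says it is unknown whether immune responses to repeat exposure will limit clinical use. The regimen to be taken forward from levels 2 to 4 gives two NSC doses in cycle 1.

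A Day-15 starter gets the second NSC dose only after the DLT window has closed. That patient can have a DLT from irinotecan or from a first NSC dose, but not one that needs a second NSC dose. Pooling such patients with those who had both doses gives a rate that describes neither group. The review trigger and the stated precision inherit the same mixture. At stake is how well the reported cycle-1 DLT rate describes the recommended regimen.

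**Working it through.** **1. Reproduce the plan's figures.** The maximum half-width of the 95% Clopper-Pearson interval over all possible counts is 0.382 for n = 6 (stated 0.38) and 0.270 for n = 14 (stated 0.27). The chance of at least one event is 1 − (1 − rate)^n: 1 − 0.75^6 = 0.822 (stated about 82%) and 1 − 0.85^14 = 0.897 (stated about 90%). All four agree.

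**2. Count patients with two NSC doses in the window.** If the six 3+3 patients are separate from the eight (Section 15.1), 6 + 4 = 10 of 14 have two doses. If the six count within the eight (Sections 5.2 and 5.4), 4 of 8 do.

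**3. Recompute for toxicity that needs a repeat dose in the window.** The upper limit with no events is 1 − 0.025^(1/n).

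| Patients | Maximum half-width | Chance of seeing a 0.15 toxicity | Upper 95% limit at 0 DLTs |
|---|---|---|---|
| 14 (as stated) | 0.270 | 89.7% | 23.2% |
| 10 of 14 | 0.313 | 80.3% | 30.8% |
| 4 of 8 | 0.432 | 47.8% | 60.2% |

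**4. Expected pooled rate.** Let p be the in-window DLT risk with both doses and q the risk in Day-15 starters. The documents give neither, so both are assumptions. The expected rate is (10p + 4q)/14 or, on the second reading, (4p + 4q)/8. For p = 0.33:

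| q | Pooled over 14 | Pooled over 8 |
|---|---|---|
| 0 | 23.6% | 16.5% |
| 0.10 | 26.4% | 21.5% |
| 0.20 | 29.3% | 26.5% |
| 0.33 (= p) | 33.0% | 33.0% |

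**5. Trigger.** 0.34 × 8 = 2.72, so it needs at least 3 DLTs in 8. The chance of firing is P(Bin(4, p) + Bin(4, q) ≥ 3), compared with P(Bin(8, p) ≥ 3) if all eight had both doses:

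| p | q = 0 | q = 0.10 | q = 0.20 | All eight with both doses |
|---|---|---|---|---|
| 0.33 | 10.8% | 23.1% | 35.9% | 52.4% |
| 0.40 | 17.9% | 31.7% | 44.9% | 68.5% |

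**6. The 3+3 stage screens first.** Six patients with both doses show at most one DLT with probability (1 − p)^6 + 6p(1 − p)^5. At p = 0.33 this is 0.090 + 0.267 = 0.358; at p = 0.40 it is 0.047 + 0.187 = 0.233. If the six and the eight are separate, passing and then not tripping the trigger at p = 0.33 has probability 0.358 × (1 − 0.108) = 0.319 with q = 0, and 0.358 × (1 − 0.231) = 0.275 with q = 0.10. With both doses in all eight it is 0.358 × (1 − 0.524) = 0.170. This product does not apply if the six are among the eight.

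**7. The 34% threshold among the four expansion patients assigned both doses.** 0.34 × 4 = 1.36, so at least 2 of 4. This is reached with probability 40.1% at p = 0.33 and 52.5% at p = 0.40. At p = 0.10 it is 1 − 0.9^4 − 4 × 0.1 × 0.9^3 = 1 − 0.656 − 0.292 = 5.2%.

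**The case against.** The delayed start is deliberate. It supplies the irinotecan-alone arm of the microdialysis comparison, and a cycle-1 DLT window is conventional. The 3+3 stage chooses the dose, and its patients must receive at least 80% of their assigned NSCs to count. The 34% rule prompts a review, not a stop, and the Protocol Management Team already reviews safety and reports quarterly. Toxicity is tabulated by course, and the stopping rule for DLT-level toxicities states no cycle limit. The only human NSC experience described, single-dose in the parent line, had no grade 3 or 4 toxicity attributed to the cells. The four patients are known in advance, so a split could be reported anyway.

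Most of this stands and sets the size of the point. It does not remove the pooling: the tables by course carry no rate or threshold, and the Analysis Plan does not call for a split.

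A reader might go further and infer three things that the documents do not support:

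- **Repeat-dose toxicity goes unseen.** The four can show it from cycle 2, and it is recorded and feeds the full toxicity profile behind the RP2D.
- **Escalation from level 2 to 3 or 3 to 4 is compromised.** Delayed starters occur only in the expansion cohort, so they do not enter those decisions.
- **The trigger must cover all cycles and allergic reactions.** That is a separate design preference. The protocol explains why allergic reactions are not DLTs and handles them through the stopping rules and Table 7.2.4.

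**Conclusion.** The point holds as a minor one, if the MTD/MFD is dose level 2, 3 or 4. Levels 1 and −1 give one NSC dose only.

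The exposure mix follows directly from the text. Its effect on the rate is conditional. If a repeat dose adds DLT risk (p above q), the pooled rate understates the regimen's cycle-1 risk and the trigger is less sensitive. If p = q, neither is affected. It would be wrong to read the pooled rate as biased for certain. The trigger contrasts rest on assumed risks that the 3+3 stage would often screen out.

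The loss of information does not depend on p or q. For toxicity needing a second dose in the window, the informative number is 10 of 14, or 4 of 8 on the overlapping count.

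A reader might also infer that the MTD decision is undermined. It is unaffected when the six 3+3 patients are separate from the eight. On the overlapping count, four Day-15 starters with only two patients outside the six would put at least two starters among the six. The documents do not reconcile the two counts.

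**What to change.** - **Analysis Plan:** make the main cycle-1 DLT rate at the RP2D, with Clopper-Pearson limits, the rate in patients assigned both Day 1 and Day 15 NSCs. Report the Day-15 starters separately and the pooled rate as secondary. Define the main group by assignment, not receipt. A patient who "Receives less than 80% of study treatments due to a toxicity related to NSCs or irinotecan" can be a DLT under the protocol, and selecting on receipt of both doses could drop that event.
- **Section 15.1:** state that for toxicity needing a repeat dose in the window the informative number is 10 of 14 (half-width 0.31; about 80% for a 0.15 toxicity), or 4 of 8 if the level-4 patients count within the eight (0.43; 48%). Say which count applies.
- **Section 5.4:** keep the 34% trigger on the cohort and also look at the same threshold among the expansion patients assigned both doses.

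The DLT definition, 3+3 rules, delayed-start comparison and sample size stay as they are. The cost is a few sentences, wider intervals, a less favourable stated figure and an occasional extra review. The look among four would be met 5.2% of the time at an assumed 10% DLT risk.
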